4.1.1 Inclusion Criteria

Dose Escalation, Maintenance Arm A

- Patients with ES-SCLC who have completed 4-6 cycles of carboplatin and etoposide induction chemotherapy, with or without *atezolizumab*, as their first-line therapy for extensive-stage disease and have responded (CR or PR) or have SD are eligible for the maintenance arm of the study.
- All side effects attributed to prior anti-cancer therapy must have resolved to Grade 1 or baseline.
- A maximum of 8 weeks (56 days) is allowed between last chemotherapy dose (Cycle 4, Day 3) given in induction and the start of maintenance therapy.

Dose Escalation, Induction Arm B

- Patients with no prior systemic treatment for ES-SCLC are eligible for this study.
- ANC \geq 1,500 cells/µL without granulocyte colony-stimulating factor support

Dose Expansion, Maintenance-Only

• Patients with ES-SCLC who have completed 4 cycles of carboplatin and etoposide induction chemotherapy and at least 3 cycles of *atezolizumab* as their first-line therapy for extensive-stage disease and have *responded* (*CR or PR*) or have SD are eligible for the maintenance arm of the study.

Dose Escalation (Arms A and B) and Dose Expansion

- Signed Informed Consent Form
- Age \geq 18 years at time of signing Informed Consent Form
- Ability to comply with the study protocol, in the investigator's judgment
- ECOG performance status of 0 or 1
- Patients must be able to swallow pills
- Histologically or cytologically confirmed diagnosis of ES-SCLC per the Veterans Administration Lung Study Group (VALG) staging system
- Patients who received prior chemoradiotherapy for limited-stage SCLC must have been treated with curative intent and experienced a treatment-free interval of at least 6 months since last chemotherapy, radiotherapy, or chemoradiotherapy cycle prior to diagnosis of ES-SCLC
- Patients with a history of treated CNS metastases that are currently asymptomatic are eligible, provided they meet all of the following criteria:
 - Only supratentorial and cerebellar metastases allowed (i.e., no metastases to midbrain, pons, medulla or spinal cord)
 - No ongoing requirement for corticosteroids as therapy for CNS disease
 - No evidence of interim progression between the completion of CNS-directed therapy and enrollment
 - Patients with new asymptomatic CNS metastases detected at the screening scan must receive radiation therapy and/or surgery for CNS metastases.

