 Following treatment, these patients may then be eligible without the need for an additional brain scan prior to enrollment, if all other criteria are met.
- Measurable disease, as defined by RECIST v1.1. Baseline measurements and evaluation of all sites of disease must be obtained ≤ 4 weeks prior to enrollment.
 - Previously irradiated lesions can only be considered as measurable disease if disease progression has been unequivocally documented at that site since radiation and the previously irradiated lesion is not the only site of disease.
- Eligible to receive a carboplatin-based chemotherapy regimen

- Adequate hematologic and end-organ function, defined by the following laboratory results obtained within 14 days prior to enrollment:
 - ANC \geq 1500 cells/ μ L (without granulocyte-colony stimulating factor support within 7 days prior to Cycle 1, Day 1)
 - Lymphocyte count \geq 500 cells/ μ L
 - Platelet count \geq 100,000 cells/µL without transfusion
 - Hemoglobin \geq 9.0 g/dL

Patients may be transfused to meet this criterion.

– INR or aPTT $\leq 1.5 \times ULN$

This applies only to patients who are not receiving the rapeutic anticoagulation; patients receiving the rapeutic anticoagulation should be on a stable dose and with INR \leq 3.5 \times ULN.

- AST (SGOT), ALT (SGPT), and alkaline phosphatase $\leq 2.5 \times ULN$ with the following exceptions:

Patients with documented liver metastases: AST and/or ALT \leq 5 \times ULN

Patients with documented bone or liver metastases: alkaline phosphatase $\leq 5 \times ULN$

- Serum total bilirubin $\leq 1.5 \times ULN$

Patients with known Gilbert disease who have serum bilirubin level \leq 3 \times ULN may be enrolled.

- Albumin $\geq 25 \text{ g/L} (2.5 \text{ g/dL})$
- Creatinine clearance (CRCL) ≥ 50 mL/min calculated with the use of the 24hour CRCL or modified Cockcroft-Gault equation (i.e., estimation of creatinine clearance rate [eCCr]) with the use of ideal body mass (IBM) instead of mass:

 $eCCr = (140-age) \times (weight in kg) \times (0.85 if female)$ 72 × (serum creatinine in mg/dL)

Or, if serum creatinine is in μ mol/L:

eCCr = $(140 - age) \times IBM$ (kg) $\times (1.04$ if female) serum creatinine (μ mol/L)

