6.5.1 Primary Efficacy Endpoint

The primary efficacy objective for the Phase Ib dose-expansion cohort is to evaluate the preliminary efficacy of venetoclax in combination with atezolizumab as maintenance therapy or venetoclax in combination with atezolizumab, carboplatin, and etoposide as induction therapy followed by venetoclax plus atezolizumab as maintenance therapy on the basis of the following endpoint:

 ORR, defined as the proportion of patients with a CR or PR on two consecutive occasions ≥4 weeks apart, as determined by the investigator according to RECIST v1.1 criteria.

Patients with no disease assessments for any reason will be classified as nonresponders. An estimate of ORR with 90% exact CI will be presented using the method of Pearson Clopper.

6.5.2 Secondary Efficacy Endpoints

The secondary efficacy objective for the Phase Ib dose-expansion cohort is to evaluate the preliminary efficacy of venetoclax in combination with atezolizumab as maintenance therapy or venetoclax in combination with atezolizumab, carboplatin, and etoposide as induction therapy or venetoclax and atezolizumab as maintenance therapy on the basis of the following endpoints:

- DOR
- PFS
- OS
- PFS rate at 6 months
- OS rate at 1 year

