Appendix 5 Response Evaluation Criteria in Solid Tumors, Version 1.1 (RECIST v1.1)

Selected sections from the Response Evaluation Criteria in Solid Tumors, Version 1.1 (RECIST v1.1), (Eisenhauer et al. 2009) are presented below, with slight modifications from the original publication and the addition of explanatory text as needed for clarity.¹

TUMOR MEASURABILITY

At baseline, tumor lesions/lymph nodes will be categorized as measurable or non-measurable as described below. All measurable and non-measurable lesions should be assessed at screening and at subsequent protocol-specified tumor assessment timepoints. Additional assessments may be performed as clinically indicated for suspicion of progression.

DEFINITION OF MEASURABLE LESIONS

Tumor Lesions

Tumor lesions must be accurately measured in at least one dimension (longest diameter in the plane of measurement is to be recorded) with a minimum size as follows:

- 10 mm by computed tomography (CT) or magnetic resonance imaging (MRI) scan (CT/MRI scan slice thickness/interval ≤5 mm)
- 10-mm caliper measurement by clinical examination (lesions that cannot be accurately measured with calipers should be recorded as non-measurable)
- 20 mm by chest X-ray

Malignant Lymph Nodes

To be considered pathologically enlarged and measurable, a lymph node must be \geq 15 mm in the short axis when assessed by CT scan (CT scan slice thickness recommended to be \leq 5 mm). At baseline and follow-up, only the short axis will be measured and followed. Additional information on lymph node measurement is provided below (see "Identification of Target and Non-Target Lesions" and "Calculation of Sum of Diameters").

¹ For clarity and for consistency within this document, the section numbers and cross-references to other sections within the article have been deleted and minor changes have been made.

DEFINITION OF NON-MEASURABLE LESIONS

Non-measurable tumor lesions encompass small lesions (longest diameter < 10 mm or pathological lymph nodes with short axis \geq 10 mm but < 15 mm) as well as truly non-measurable lesions. Lesions considered truly non-measurable include leptomeningeal disease, ascites, pleural or pericardial effusion, inflammatory breast disease, lymphangitic involvement of skin or lung, peritoneal spread, and abdominal mass/abdominal organomegaly identified by physical examination that is not measurable by reproducible imaging techniques.

SPECIAL CONSIDERATIONS REGARDING LESION MEASURABILITY

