To reiterate, however, if the radiologist is able to provide an actual measurement, that should be recorded, even if it is <5 mm, and in that case "too small to measure" should not be ticked.

Measuring Lesions That Split or Coalesce on Treatment

When non–lymph node lesions fragment, the longest diameters of the fragmented portions should be added together to calculate the sum of diameters. Similarly, as lesions coalesce, a plane between them may be maintained that would aid in obtaining maximal diameter measurements of each individual lesion. If the lesions have truly coalesced such that they are no longer separable, the vector of the longest diameter in this instance should be the maximum longest diameter for the coalesced lesion.

EVALUATION OF NON-TARGET LESIONS

Measurements are not required for non-target lesions, except that malignant lymph node non-target lesions should be monitored for reduction to <10 mm in short axis. Non-target lesions should be noted at baseline and should be identified as "present" or "absent" and (in rare cases) may be noted as "indicative of progression" at subsequent evaluations. In addition, if a lymph node lesion shrinks to a non-malignant size (short axis <10 mm), this should be captured on the CRF as part of the assessment of non-target lesions.

RESPONSE CRITERIA

CRITERIA FOR TARGET LESIONS

Definitions of the criteria used to determine objective tumor response for target lesions are provided below:

• Complete response (CR): Disappearance of all target lesions

Any pathological lymph nodes must have reduction in short axis to <10 mm.

- Partial response (PR): At least a 30% decrease in the sum of diameters of all target lesions, taking as reference the baseline sum of diameters, in the absence of CR
- Progressive disease (PD): At least a 20% increase in the sum of diameters of target lesions, taking as reference the smallest sum of diameters at prior timepoints (including baseline)

In addition to the relative increase of 20%, the sum of diameters must also demonstrate an absolute increase of \geq 5 mm.

 Stable disease (SD): Neither sufficient shrinkage to qualify for CR or PR nor sufficient increase to qualify for PD
CRITERIA FOR NON-TARGET LESIONS

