Definitions of the criteria used to determine the tumor response for the group of nontarget lesions are provided below. While some non-target lesions may actually be measurable, they need not be measured and instead should be assessed only qualitatively at the timepoints specified in the schedule of activities.

CR: Disappearance of all non-target lesions and (if applicable) normalization of tumor marker level

All lymph nodes must be non-pathological in size (< 10 mm short axis).

- Non-CR/Non-PD: Persistence of one or more non-target lesions and/or (if applicable) maintenance of tumor marker level above the normal limits
- PD: Unequivocal progression of existing non-target lesions

SPECIAL NOTES ON ASSESSMENT OF PROGRESSION OF NON-TARGET LESIONS

Patients with Measurable and Non-Measurable Disease

For patients with both measurable and non-measurable disease to achieve unequivocal progression on the basis of the non-target lesions, there must be an overall level of substantial worsening in non-target lesions in a magnitude that, even in the presence of SD or PR in target lesions, the overall tumor burden has increased sufficiently to merit discontinuation of therapy. A modest increase in the size of one or more non-target lesions is usually not sufficient to qualify for unequivocal progression status. The designation of overall progression solely on the basis of change in non-target lesions in the face of SD or PR in target lesions will therefore be extremely rare.

NEW LESIONS

The appearance of new malignant lesions denotes disease progression; therefore, some comments on detection of new lesions are important. There are no specific criteria for the identification of new radiographic lesions; however, the finding of a new lesion should be unequivocal, that is, not attributable to differences in scanning technique, change in imaging modality, or findings thought to represent something other than tumor (for example, some "new" bone lesions may be simply healing or flare of preexisting lesions). This is particularly important when the patient's baseline lesions show PR or CR. For example, necrosis of a liver lesion may be reported on a CT scan report as a "new" cystic lesion, which it is not.

A lesion identified during the study in an anatomical location that was not scanned at baseline is considered a new lesion and will indicate disease progression.

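### Complete responders are called eligible for the maintenance cohorts, but the measurable-disease criterion excludes them and the ORR has no scoring rule for them

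*Combined protocol and SAP*

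**What the plan says.** Section 4.1.1 gives cohort-specific criteria first. For Arm A, patients who have finished first-line induction and "have responded (CR or PR) or have SD are eligible for the maintenance arm of the study". The maintenance-only expansion criterion admits the same three categories, and there the words naming CR and PR are italicised, the protocol's mark for substantive new information.

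A common block follows, headed "Dose Escalation (Arms A and B) and Dose Expansion". It includes: "Measurable disease, as defined by RECIST v1.1. Baseline measurements and evaluation of all sites of disease must be obtained ≤ 4 weeks prior to enrollment". No exception is made for the maintenance cohorts. The synopsis repeats both statements.

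Appendix 5 defines the terms. For target lesions: "Complete response (CR): Disappearance of all target lesions", with any pathological node reduced to under 10 mm in short axis. For non-target lesions: "CR: Disappearance of all non-target lesions and (if applicable) normalization of tumor marker level". A measurable tumour lesion is at least 10 mm on CT or MRI, and a measurable node is at least 15 mm in short axis.

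Section 6.5 makes all enrolled expansion patients the efficacy population, and Section 6.5.1 makes confirmed ORR the primary efficacy endpoint.

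**The concern.** The two eligibility statements cannot both be true of a patient in CR. A site has to choose one, and the choice decides who enters the trial.

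In the maintenance-only expansion the choice reaches the primary efficacy endpoint. A patient with no lesions at baseline has no sum of diameters from which a partial response could be measured. Nor is there anything left to disappear, so a new complete response cannot be observed. The all-enrolled denominator would still count that patient.

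In Arm A, which has no efficacy endpoint, the question is narrower: patients whom the text invites may be turned away by a criterion whose purpose in that arm is not explained.

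**Working it through.** **1. Can a patient in CR have measurable disease?** Set the Appendix 5 thresholds side by side.

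| Feature | In CR | Measurable |
|---|---|---|
| Non-nodal target lesion | gone | at least 10 mm (CT/MRI) |
| Node, short axis | under 10 mm | at least 15 mm |
| Non-target lesions | gone | not applicable |

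The ranges do not overlap. A patient whose lesions have regrown to measurable size by the maintenance baseline has progressed and is no longer in CR. Section 4.1.1 does not name the criteria for the induction response, but Appendix 5 is the only definition of CR in the documents.

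**2. How would such a patient be scored?** Appendix 5 has one overall-response table for patients with target lesions and one for patients with non-target lesions only. Neither covers a patient with no lesions. PR needs a 30% fall from a baseline sum, which does not exist here. Two scorings are therefore open: non-responder, or continued absence of disease recorded as CR.

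**3. The plan's own figure.** Section 6.1 takes 20 patients and an observed maintenance-only ORR of 5%, that is 1/20. The exact (Clopper-Pearson) interval has lower limit Beta(α/2; x, n−x+1) and upper limit Beta(1−α/2; x+1, n−x). With x = 1, n = 20 and 80% confidence it is 0.53% to 18.1%, which matches the 1% to 18% in Table 13. That calculation treats all 20 patients as able to respond.

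**4. Illustration with two entrants in CR and one true responder** (90% exact intervals, the level set in Section 6.5.1):

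- Scored as non-responders: 1/20 = 5.0% (0.3% to 21.6%).
- Continued absence of disease scored as CR: (1 + 2)/20 = 3/20 = 15% (4.2% to 34.4%).
- Measurable patients only: 1/(20 − 2) = 1/18 = 5.6% (0.3% to 23.8%).

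**5. Range over the assumed number, k, entering in CR.** The documents give no CR rate after atezolizumab plus carboplatin and etoposide. The only figure, in Section 1.2, is above 40% for cisplatin and etoposide in older studies, and 0.40 × 20 = 8. So k is run from 0 to 8, with a true rate of 5% in measurable patients and n = 20 − k.

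| k | Expected ORR if entrants are non-responders, 0.05 × n/20 | Chance of any true responder, 1 − 0.95^n | ORR if entrants are scored CR and one patient truly responds, (1 + k)/20 |
|---|---|---|---|
| 0 | 5.0% | 64.2% | 5% |
| 2 | 4.5% | 60.3% | 15% |
| 4 | 4.0% | 56.0% | 25% |
| 8 | 3.0% | 46.0% | 45% |

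**The case against.** The strongest reply is that inclusion criteria are cumulative. Section 4.5.1 requires every criterion to be confirmed before enrollment, and Section 9.2 bars eligibility waivers. On that reading complete responders are excluded, a patient enrolled in CR is a deviation to be summarised under Section 6.2, and ORR is untouched. This stands as the more orderly reading. It does not remove the contradiction, because the statement that complete responders are eligible is then false in both cohorts. Since the expansion wording is marked as new text, a site could reasonably take it as intended.

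The ORR consequence is also conditional. Under Section 3.1.5 the maintenance-only expansion opens only if toxicity prevents an induction RP2D from being identified. This stands in full.

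Three stronger readings are tempting, and the documents do not support them:

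- A reader might infer that ORR is biased downward. With no scoring rule the direction is not fixed, and the upward error can be the larger one.
- A reader might take the Section 6.5.1 rule, "Patients with no disease assessments for any reason will be classified as nonresponders", as settling the scoring. It covers patients who are never assessed. Complete responders would be scanned every 6 weeks, so it does not reach them.
- A reader might call Arm A a safety-only cohort that excludes complete responders without need. Arm A also has pharmacokinetic, immunogenicity and biomarker objectives (Sections 2.1.2 to 2.1.4), the last including relationships with efficacy, and it has scheduled tumour assessments. What can be said is that it has no efficacy endpoint and is outside the efficacy population, although Section 6.1 blurs this by labelling the maintenance-only ORR as Arm A.

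Finally, the dilution alone is small: 5.0% against 5.6% is well inside the interval around 1/20, and Section 6.1 sets no test or threshold for it to cross. That is fair. The 15% reading is the more serious possibility.

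**Conclusion.** The contradiction is real, sits in the current text of both Section 4.1.1 and the synopsis, and follows from the protocol's own definitions rather than from any assumed figure.

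Its effect on the primary endpoint depends on two conditions: that sites act on the CR wording, and that the maintenance-only expansion opens. If both hold, ORR is undefined for some patients in its denominator. In the two-patient illustration the same data could be reported as 5% or 15%. The number of entrants in CR and the single true responder are assumptions. If the criteria are applied jointly, ORR is unaffected and what remains is a false eligibility statement. The point merits correction because the change is cheap and the primary endpoint may be exposed.

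**What to change.** In Section 4.1.1 and the synopsis, remove CR from the maintenance-only expansion criterion and keep the requirement for RECIST v1.1 measurable disease at the maintenance baseline. Every patient in the all-enrolled ORR denominator can then be scored for response. Keeping CR and adding a scoring rule to Section 6.5.1 would also end the ambiguity, but it would leave patients in the denominator who have no lesion in which a response could be seen.

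For Arm A, state expressly whether the measurable-disease criterion applies to complete responders. With no efficacy endpoint there, either answer is workable, but the text must give one.

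The cost is eligibility wording, with no change to sample size, procedures or treatment. The small downside is that complete responders cannot join the ORR expansion.

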Once the *RP2D* in the induction and in the maintenance *phase* has been established from the dose-escalation cohorts, additional patients will be enrolled in the dose-expansion cohort to further assess the safety and efficacy of venetoclax in combination with carboplatin, etoposide and/or atezolizumab. If the RP2D for venetoclax during induction was established, then the dose-expansion cohort will continue to test venetoclax in both induction and maintenance. If significant toxicity and DLTs in induction preclude identification of an RP2D for venetoclax in induction treatment, then the safety and efficacy of venetoclax will only be investigated in dose-expansion in the maintenance setting. If the maintenance-only cohort is expanded, then prior treatment with 4 induction cycles of carboplatin and etoposide as well as at least 3 cycles of *atezolizumab* will be required. If there are concerns about the tolerability of venetoclax during the dose-expansion stage, then a lower dose or alternative dosing schedule may be explored based on the severity and timing of DLTs as well as the specific adverse events encountered. For example, consideration may be given to enrolling an expansion cohort at the next lower dose level (as defined in dose-escalation stage; see Section 3.1.2). Decision making will integrate cumulative safety and efficacy data during treatment and will be led by the Medical Monitor in consultation with the Principal Investigators and a committee composed of at a minimum the following Sponsor representatives: statistician, safety scientist, PK scientist, and clinical scientist.

DOR=duration of response; ECOG=Eastern Cooperative Oncology Group; ES=extensive-stage; INV=investigator; MTD=maximum tolerated dose; ORR=objective response rate; PFS=progression-free survival; Q3W=every 3 weeks; RECIST v1.1=Response Evaluation Criteria in Solid Tumors, Version 1.1; RP2D-I=recommended Phase II dose for induction; RP2D-M=recommended Phase II dose for maintenance; SCLC=small cell lung cancer.

3.1.6 Treatment after Disease Progression

During the study, patients who meet criteria for disease progression per RECIST v1.1 and show evidence of clinical benefit may continue treatment at the investigator's discretion, provided that the patients meet all of the following criteria:

- Evidence of clinical benefit, as assessed by the investigator

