6.5.2.2 Progression-Free Survival

PFS after enrollment is defined as the time from enrollment to the first occurrence of disease progression or relapse or death from any cause (whichever occurs first), as determined by the investigator according to RECIST v1.1 criteria. Data for patients without the occurrence of disease progression or death as of the clinical data cutoff date will be censored at the time of last tumor assessment (or the time of enrollment plus 1 day if no tumor assessment was performed after the baseline visit).

The Kaplan-Meier approach will be used to estimate median PFS. The Kaplan-Meier curve of time to PFS will be provided.

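### The maintenance-only expansion has neither Arm A's 56-day limit since chemotherapy nor its toxicity-recovery criterion, so PFS and OS from enrollment may depend on an uncontrolled entry time

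*Combined protocol and SAP*

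**What the plan says.** Section 4.1.1 lists inclusion criteria under separate cohort headings, and the synopsis repeats the arrangement.

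- **Dose Escalation, Maintenance Arm A** has three bullets. The first requires 4–6 cycles of carboplatin and etoposide, with or without atezolizumab, and response or stable disease. The second is a recovery rule: "All side effects attributed to prior anti-cancer therapy must have resolved to Grade 1 or baseline". The third limits how long before maintenance begins chemotherapy may have ended: "A maximum of 8 weeks (56 days) is allowed between last chemotherapy dose (Cycle 4, Day 3) given in induction".
- **Dose Expansion, Maintenance-Only** has one bullet: "Patients with ES-SCLC who have completed 4 cycles of carboplatin and etoposide induction chemotherapy and at least 3 cycles of" (the drug meant is atezolizumab), with response or stable disease.

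Section 3.1.5 restates the prior-therapy requirement, again for atezolizumab and again without an interval or a recovery rule: "If the maintenance-only cohort is expanded, then prior treatment with 4 induction cycles of carboplatin and etoposide as well as at least 3 cycles of" (the drug name follows). It opens this cohort only if toxicity in induction prevents an induction RP2D from being identified. The criteria shared by all cohorts and the exclusions in Section 4.1.2 contain neither a limit on time since induction nor a general recovery rule.

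The efficacy population is the expansion cohort (Section 6.5). On the time origin, Section 6.5.2.2 states: "PFS after enrollment is defined as the time from enrollment to the first occurrence of" progression, relapse or death. OS also runs from enrollment (Section 6.5.2.3), and the 6-month PFS and 1-year OS rates are Kaplan-Meier estimates with 90% intervals (Sections 6.5.2.4 and 6.5.2.5).

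**The concern.** A patient many months into atezolizumab maintenance without progression fits the expansion bullet but would be too late for Arm A. RP2D-M is set in Arm A, in patients bound by both rules, and is then applied to a cohort bound by neither.

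A patient who enters late has already been event-free for some time, and enrollment resets the clock. If prognosis varies between patients, late entrants are the better-prognosis remainder, and PFS and OS from enrollment look longer than they would for patients entering soon after induction. The plan has no adjustment for time since induction and does not report it, so a reader could not tell how much of a result reflects entry time. If this cohort opens, it is the study's only expansion evidence on efficacy.

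The missing recovery rule raises a different question. Toxicity left over from induction could be present at the start and blur the reading of safety at RP2D-M.

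**Working it through.** **1. Plan figures.** The expansion is sized only on ORR. Exact 80% Clopper-Pearson intervals for 1, 2, 14, 15 and 16 responders of 20 are (0.5, 18.1), (2.7, 24.5), (53.3, 83.4), (58.5, 87.3) and (63.9, 91.0)%, which match Table 13 on rounding. No figure is given for PFS or OS, and nothing below changes Table 13.

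**2. Latest entry if the Arm A limit applied.** Cycle 4, Day 3 is day 3 × 21 + 3 = 66 without delays. Adding 56 gives day 122, or 122/30.44 = 4.0 months after induction start. The expansion list sets no such bound.

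**3. Effect of entry time.** For entry at t0 and horizon h, the rate counted from enrollment is S(t0 + h)/S(t0). Section 1.2 gives medians of 5.2 months (PFS) and 12.3 months (OS) for atezolizumab plus chemotherapy, from a trial that randomized before induction. The hazard shape is not in the documents, so it is assumed and varied:

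- exponential: S = 2^(−t/median);
- gamma frailty with variance θ: S = (1 + θΛt)^(−1/θ), Λ = (2^θ − 1)/(θ × median);
- Weibull with shape k: S = exp(−ln 2 × (t/median)^k).

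Example with θ = 1, where S = 1/(1 + t/5.2): entry at 4.0 months gives (5.2 + 4.0)/(5.2 + 4.0 + 6) = 9.2/15.2 = 61%; entry at 12 months gives 17.2/23.2 = 74%.

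| Assumed shape | 6-month PFS, entry at 4.0 / 9 / 12 months | 1-year OS, entry at 4.0 / 9 / 12 months |
|---|---|---|
| Exponential (constant) | 45 / 45 / 45% | 51 / 51 / 51% |
| Frailty 0.5 (falling) | 54 / 61 / 65% | 54 / 58 / 60% |
| Frailty 1.0 (falling) | 61 / 70 / 74% | 58 / 64 / 67% |
| Weibull 0.8 (falling) | 54 / 58 / 60% | 56 / 59 / 60% |
| Weibull 1.3 (rising) | 32 / 26 / 24% | 44 / 40 / 38% |

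If every patient entered at 9–12 months instead of 4.0, a falling hazard adds about 4–14 points to 6-month PFS and 3–9 points to 1-year OS. A constant hazard adds nothing. The rising hazard subtracts about 6–8 and 5–7 points.

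**4. A second assumption.** Take PFS after induction as a mixture of two exponentials, with entry at 1.8 months (56 days), 6 and 9 months after last chemotherapy. With 80% at median 3 months and 20% at median 12, 6-month PFS from entry is 36.6, 43.9 and 49.8%. With 70% at median 3 and 30% at median 18, it is 45.5, 56.3 and 63.5%. The largest shift is 63.5 − 45.5 = 18 points, again only if everyone enters late.

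**5. Only some patients enter late.** In these mixtures the share still progression-free at 9 months is 0.8 × 0.125 + 0.2 × 0.595 = 22%, and 0.7 × 0.125 + 0.3 × 0.707 = 30%. Suppose, as an assumption, that a quarter of the cohort enters late and the rest at the 56-day limit:

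- 80/20 mixture: 0.75 × 36.6 + 0.25 × 49.8 = 39.9%, up 3.3 points;
- 70/30 mixture: 0.75 × 45.5 + 0.25 × 63.5 = 50.0%, up 4.5 points;
- frailty 1.0, late entry at 12 months: (74.1 − 60.5)/4 = up 3.4 points;
- Weibull 1.3, late entry at 12 months: (24.0 − 32.3)/4 = down 2.1 points.

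Of 20 patients, 4.5 points is 0.9 of a patient. Ignoring censoring, the 90% half-width at 37% is 1.645 × √(0.37 × 0.63/20) = 18 points.

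**The case against.** The best defence is that the omission is a drafting slip with little consequence.

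- **Intent.** The synopsis describes the required atezolizumab as given together with the four induction cycles, so the minimum of 3 may only allow for a missed dose. Section 6.1 labels the maintenance-only setting Arm A. Both suggest that Arm A's rules were meant to carry over. This stands as evidence of intent, but neither text sets a time limit, and Section 4.1.1 gives the cohort its own heading and a different prior-therapy rule. A site will apply the bullets under that heading.
- **Endpoints.** PFS and OS are secondary, descriptive and without a stated benchmark. The primary endpoint is ORR, measured from a baseline taken within 4 weeks before enrollment, and no effect on it is shown. This stands and limits the weight of the point.
- **Recovery.** All cohorts must meet "Adequate hematologic and end-organ function, defined by the following laboratory results obtained within 14 days prior to enrollment" and have ECOG 0 or 1. Drug-induced or active pneumonitis is excluded, as are findings that put the patient at high risk of complications, and Section 4.5 ties each dose to acceptable clinical and laboratory findings. This covers much of the gap, but not residual non-laboratory toxicity in general, such as neuropathy.

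A reader might infer that the results will be inflated by up to 18 points, or cannot be interpreted against Arm A. The documents support neither. Inflation needs a falling hazard, which no section establishes; 18 points needs every patient to enter late; and no efficacy comparison with Arm A is planned.

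**Conclusion.** The point holds as a gap in eligibility with a possible, unquantified effect on secondary endpoints. As written, the maintenance-only expansion can enroll patients long after induction, a different population from the one in which RP2D-M is set. PFS, OS and their landmark rates may then shift with entry time, in a direction that depends on how the hazard changes after induction.

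The size cannot be derived from the documents. The calculations rest on assumed hazard shapes, on medians from a trial that randomized before induction, and on an assumed share of late entrants. If only some patients enter late, a shift of a few points is more likely than 18, and it would lie well inside the interval that 20 patients give. The recovery gap is narrower and bears mainly on the interpretation of safety. Everything is conditional on the cohort opening. The case for acting is that the correction is cheap and removes a source of selection that the plan neither controls nor reports.

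**What to change.** 1. In Section 4.1.1 and the synopsis, reconcile the two cohort lists so that Arm A's existing interval and recovery criteria also bind the maintenance-only expansion, or state why the cohorts differ.
2. Add time from last induction chemotherapy to enrollment to the baseline summaries for this cohort, and report it alongside PFS, OS and their landmark rates.
3. In the same edit, reconcile Section 4.1.2, which excludes prior anti-PD-L1 therapy, with this cohort's required prior atezolizumab. Read literally, that exclusion bars every patient who meets the inclusion bullet.

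The cost is a short text change and one baseline summary. If the criteria are extended, the recruitment pool for this cohort becomes slightly narrower. No sample-size figure changes.
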